8.3 Evaluating Adverse Events

AEs will be evaluated by an investigator who is a qualified medical physician.

8.3.1 Determining AE Severity and Grade

AE severity and grade will be evaluated according to the Common Terminology for Adverse Events (CTCAE), version 5.0. Any AE which changes CTCAE grade over the course of a given episode should be closed at the date the severity changed and a new AE recorded on the AE case report forms from that date at the new severity.

8.3.2 Determining AE Causality

The Investigator must endeavour to obtain sufficient information to assess the causality of the AE and must provide his/her opinion whether the event has any relationship to the administered study treatment / procedure. This may require instituting supplementary investigations of significant AEs based on their clinical judgement of the likely causative factors and/or include seeking a further opinion from a specialist in the field of the AE.

Causality is the relationship of an AE to the IMP and will be determined as follows:

Definite:	
• There is clear evidence to suggest a causal relationship.• Starts within a time related to the IMP administration and• No obvious alternative medical explanation.
Probable:	
• There is evidence to suggest a causal relationship• Starts within a time related to the IMP administration and• Cannot be reasonably explained by known characteristics of the patient's clinical state.
Possible:	
• A causal relationship between the IMP and the AE is at least a reasonable possibility.• Starts within a time related to the IMP administration• However, the influence of other factors may have contributed to the event (e.g. the patient's clinical condition, other concomitant treatments).
Unlikely:	
• There is little evidence to suggest there is a causal relationship.• There is another reasonable explanation for the event (e.g. the patient's clinical condition, other concomitant treatment).• The time association is such that the trial drug is not likely to have had an association with the observed effect.
Not related:	
• The AE is definitely not associated with the IMP administered.

8.4 Serious adverse events (SAEs)

An SAE is defined as any untoward medical occurrence or effect that at any dose that:

- Results in death;
- Is life-threatening or places the patient, in the view of the investigator, at immediate risk of death from the event as it occurred¹;
- Requires in-patient hospitalisation or prolongs existing in-patient hospitalisation²

- Results in persistent or significant incapacity or disability;
- Is a new cancer
- Is a congenital anomaly or birth defect;
- Is associated with an overdose (whether accidental or intentional). Any AE associated with an overdose is considered a SAE.
- Is any other medically important event.³

¹ This does not include an AE which hypothetically might have caused death if had it occurred in a more severe form.

² Hospitalisation is defined as an unexpected inpatient admission, regardless of length of stay, even if the hospitalisation is a precautionary measure for continued observation. It does not usually apply to scheduled admissions that were planned before study inclusion or visits to casualty (without admission).

³ A medically important event may not result in death, not be life threatening, or not require hospitalisation but may be considered a SAE when, based upon appropriate medical judgment, the event that may jeopardise the patient and require medical or surgical intervention to prevent one of the outcomes listed above.

8.4.1 Reporting SAEs

All SAEs regardless of causality, pregnancy or overdose that occur from the time of consent through 90 days following cessation of study treatment or 30 day following cessation of study treatment if the participant initiates a new anticancer therapy, whichever is earlier, must be reported on the SAE report form within 24 hours of the investigator / designee becoming aware of the event.

The SAE/ECI report form should be sent to
 Email: [contact]
 [contact]
 who will in turn notify MSD of the event.

The SAE form must be completed, assessed for causality and expectedness against the current version of the Investigator Brochure, then signed and dated by the Principal Investigator or an appropriately qualified designated individual identified on the delegation log. The report will then be reviewed by the Chief Investigator (or a nominated representative) to confirm relatedness and expectedness. The CTCAE version 5.0 must be used to grade each SAE, and the worst grade recorded. If new or amended information on a previously reported SAE becomes available, the Investigator should report this to the Sponsor (via RM-CTU) on a new SAE report form. The Sponsor (via RM-CTU) will in turn submit the updated report to MSD. Please refer to the SAE completion guidelines for further information.

Additionally, any SAE considered by an investigator who is a qualified physician to be related to the IMP or protocol-specified procedure that is brought to the attention of the investigator at any time outside of the time period specified in the previous paragraph also must be reported immediately to the Sponsor (via RM-CTU) who will inform MSD.

8.4.2 Events exempt from being reported as SAEs

Events specified in this section do not require reporting as SAEs in this trial, unless hospitalisation is prolonged for any reason and then an SAE form must be completed. The events must still be recorded in the appropriate section of the CRF.

1. Elective admissions to hospital for procedures which were planned and documented in the medical records at the time of consent are not SAEs, and do not require SAE reporting.
2. Hospitalisation for administration of the IMP, or to facilitate study procedures such as pharmacokinetic sampling according to the trial protocol, is also exempt from being reported as an SAE.
3. Progressive disease is not considered a SAE unless the patient requires in-patient hospitalisation or prolonged existing in-patient hospitalisation or death but will be reported in the CRFs

8.4.3 Determining SAE Causality and Expectedness

Assessment of causality and expectedness for all SAEs will be made by the PI/designee and Chief Investigator or delegate against the Investigator's Brochure (IB) (Reference Safety Information contained within the IB). If updated versions of the IB are released during the course of the trial then assessment of expectedness will be made against the current regulatory approved version. The IB as last amended and approved by the national competent authority serves as the reference safety information for the assessment of the expectedness of any adverse reaction that might occur during the clinical trial. The expected side effects from thoracic SBRT include: Shortness of breath, cough, chest pain (including rib fracture), skin reactions where the beams entry the body, tiredness, pain on swallowing, scarring and local inflammatory changes around treatment site and longer term reduction in breathing capacity.

8.5 Events of Clinical Interest

8.5.1 Definitions of Evidence of Clinical Interest (ECI)

Selected non-serious and SAEs can also be classified as Events of Clinical Interest (ECI) and overdose and liver toxicity ECIs and must be reported as described in section 8.5.2.

Events of clinical interest for this trial include:

1. An overdose of pembrolizumab, as defined in Section 0 that is not associated with clinical symptoms or abnormal laboratory results.
2. A Drug induced liver injury (DILI) defined as elevated AST or ALT lab value that is greater than or equal to 3X the upper limit of normal

AND / OR

An elevated total bilirubin lab value that is greater than or equal to 2X the upper limit of normal

AND / OR

An alkaline phosphatase lab value that is less than 2X the upper limit of normal, as determined by way of protocol-specified laboratory testing or unscheduled laboratory testing.

3. Any AEs identified in the below Table 12 can be classified as immune-related events of clinical interest. A detailed narrative of overdose and liver toxicity ECIs should be reported as described in section 8.5.2

Patients should be assessed for possible ECIs prior to each dose. Lab results should be evaluated and patients should be asked for signs and symptoms suggestive of an immune-related event. Patients who develop an ECI thought to be immune-related should have additional testing to rule out other etiologic causes. If lab results or symptoms indicate a possible immune-related ECI, then additional testing should be performed to rule out other etiologic causes. If no other cause is found, then it is assumed to be immune-related.

8.5.2 Reporting of ECIs

Overdose and liver toxicity ECIs whether or not related to the pembrolizumab, occurring from the first dose until 30 days following the last treatment dose, or the initiation of a new anticancer therapy, whichever is earlier, must be recorded on the AE e-case report forms and reported using the SAE/ECI report form within 24 hours of the PI/designee becoming aware of the event to the Sponsor (via RM-CTU) as follows:

The SAE / ECI report form should be sent to
Email: [contact]
[contact]
who will in turn notify MSD of the event.

When reporting an ECI or an overdose using the SAE report form, it should be clarified whether or not the ECI or overdose is also considered an SAE.

Table 12: Immune related AEs considered ECIs

Pneumonitis - (classified as ECI if \geq Grade 2)		
Acute interstitial Pneumonitis	Interstitial Lung Disease	Pneumonitis
Colitis - (classified as ECI if \geq Grade 2 or any grade resulting in dose modification or use of systemic steroids to treat the AE)		
Intestinal Obstruction	Colitis	Colitis microscopic
Enterocolitis	Enterocolitis hemorrhagic	Gastrointestinal perforation
Necrotising colitis	Diarrhoea	
Endocrine - (classified as ECI if \geq Grade 3 or \geq Grade 2 and resulting in dose modification or use of systemic steroids to treat the AE)		
Adrenal Insufficiency	Hyperthyroidism	Hypophysitis
Hypopituitarism	Hypothyroidism	Thyroid disorder
Thyroiditis	Hyperglycemia, if \geq Grade 3 and associated with ketosis or metabolic acidosis (DKA)	
Type 1 diabetes mellitus (if new onset)		
Hematologic - (classified as ECI if \geq Grade 3 or any grade resulting in dose modification or use of systemic steroids to treat the AE)		
Autoimmune haemolytic anaemia	Aplastic anaemia	Thrombotic thrombocytopenic purpura
Idiopathic thrombocytopenia purpura	Disseminated intravascular coagulation	Haemolytic uraemic syndrome
Any grade 4 anaemia regardless of underlying mechanism		
Hepatic - (classified as ECI if \geq Grade 2 or any grade resulting in dose modification or use of systemic steroids to treat the AE)		
Hepatitis	Autoimmune hepatitis	Transaminase elevations (Alton/or AST)
Infusion reactions - (classified as ECI for any grade)		
Allergic reaction	Anaphylaxis	Cytokine release syndrome
Serum sickness	Infusion reactions	Infusion-like reactions
Neurologic - (classified as ECI for any grade)		
Autoimmune neuropathy	Guillain-Barre syndrome	Demyelinating polyneuropathy
Myasthenic syndrome		
Ocular - (classified as ECI if \geq Grade 2 or any grade resulting in dose modification or use of systemic steroids to treat the AE)		
Uveitis	Iritis	
Renal - (classified as ECI for \geq Grade 2)		
Nephritis	Nephritis autoimmune	Renal Failure
Renal failure acute	Creatinine elevations - (report as ECI if \geq Grade 3 or any grade resulting in dose modification or use of systemic steroids to treat the AE)	
Skin - (classified as ECI for any grade)		
Dermatitis exfoliate	Erythema multiforme	Stevens-Johnson Syndrome
Toxic epidermal necrolysis		
Skin - (classified as ECI for \geq Grade 3)		
Pruritus	Rash	Rash generalised
Rash maculo-papular	Any rash clinical significant in the physicians judgement.	
Other - (classified as ECI for any grade)		
Myocarditis	Pancreatitis	Percarditis
Any other grade 3 event which is considered immune-related by the physician.		

8.6 Definition of an Overdose for this Protocol and Reporting of Overdose

At present no specific information is available on the treatment of overdose of pembrolizumab. For purposes of this trial, an overdose will be defined as any dose exceeding the prescribed dose for pembrolizumab by 20%. In the event of overdose the patient should be observed closely for signs of toxicity. Appropriate supportive treatment should be provided if clinically indicated.

If an AE(s) is associated with (“results from”) the overdose of pembrolizumab, the AE(s) should be recorded on the AE CRF and reported as a SAE, even if no other seriousness criteria are met.

If an overdose is taken without any associated clinical symptoms or abnormal laboratory results, the overdose is again recorded as an AE on the CRF and reported as a non-serious ECI, using the terminology “accidental or intentional overdose without adverse effect.”

All reports of overdose either SAE or ECI must be reported within 24 hours of the PI or designee becoming aware of the event to the Sponsor (via RM-CTU) as follows:

The SAE / ECI report form should be sent to
Email: [contact]
[contact]
who will in turn notify MSD of the event.

When reporting an ECI or an overdose using the SAE report form, it should be clarified whether or not the ECI or overdose is also considered an SAE.

8.7 Reporting of Pregnancy and Lactation

Although pregnancy and lactation are not considered AEs, it is the responsibility of investigators or their designees to report any pregnancy or lactation in a patient (spontaneously reported to them), that occurs during the trial or within 120 days of completing the trial, or 30 days following cessation of treatment if the patient initiates new anticancer therapy, whichever is earlier. All patients who become pregnant must be followed to the completion/termination of the pregnancy. Pregnancy outcomes of spontaneous abortion, missed abortion, benign hydatidiform mole, blighted ovum, foetal death, intrauterine death, miscarriage and still birth must be reported as SAE (Important Medical Events). If the pregnancy continues to term, the outcome (health of infant) must also be reported with the parents' consent. Such events must be reported within 24 hours to the Sponsor (via RM-CTU) as follows:

The SAE / ECI report form should be sent to
Email: [contact]
[contact]
who will in turn notify MSD of the event.

8.8 Definition of a Serious Adverse Reaction (SAR)

A SAR is defined as an SAE that is judged to be related to any dose of study drug administered to the patient.

8.9 Definition of Suspected, Unexpected, Serious, Adverse Reactions (SUSARs)

A SUSAR is a serious adverse reaction, the nature or severity of which is not consistent with the applicable product information (e.g. reference safety information appendices of investigator's brochure for an unauthorised investigational product or summary of product characteristics for an authorised product).

8.10 Reporting of SUSARs

All SUSARs must be reported using the SAE report form within 24 hours of the PI/designee becoming aware of the event to the Sponsor (via RM-CTU) as follows:

The SAE / ECI report form should be sent to

Email: [contact]

[contact]

who will in turn notify MSD, relevant Independent Ethics Committee (IEC) / Institutional review, appropriate regulatory authorities and the participating Principal Investigators of the event.

The Sponsor (via RM-CTU) will in turn notify the MSD, relevant Independent Ethics Committee (IEC) / Institutional review, appropriate regulatory authorities and the participating Principal Investigators in accordance with regulatory requirements and within the timelines as defined below:

- For fatal and life-threatening SUSARs the Sponsor (via RM-CTU) should report at least the minimum information as soon as possible and in any case no later than seven days after being made aware of the case.
- SUSARs which are not fatal and not life-threatening are to be reported within 15 days

Follow up of patients who have experienced a SUSAR should continue until recovery is complete or the condition has stabilised.

8.11 Annual Reporting of Serious Adverse Events

The Development Safety Update Report (DSUR) will be submitted annually within 60 days of the anniversary of regulatory approval for the trial. This report will be submitted to regulatory authorities and Independent Ethics Committees (IEC) in accordance with all applicable global laws and regulations. The DSUR will be prepared by the sponsor in collaboration with RM-CTU. It will be submitted by the Sponsor and copies will be forwarded to RM-CTU, MSD and Investigators.

8.12 Urgent Safety Measures

The Sponsor or Investigator may take appropriate urgent safety measures (USMs) in order to protect the patient of a clinical trial against any immediate hazard to their health or safety. This includes procedures taken to protect patients from pandemics or infections that pose serious risk to human health.

USMs may be taken without prior notification from the competent authority. However the CI/delegate must notify the Medicines and Healthcare Products Regulations (MHRA), the Research Ethics Committee (REC) and the Sponsor (via RM-CTU) of the new events and the measures taken and the plan for further action within 3 days of the measure being implemented. Should the site initiate a USM, the Investigator must inform the Sponsor (via RM-CTU) immediately either by:

Email: [contact]

[contact]

[contact]

The notification must include:

- The date of the USM;
- Who took the decision; and
- Why action was taken.

RM-CTU will notify the MHRA, REC and the Sponsor immediately by telephone and within 3 days in writing of USM initiation. RM-CTU will distribute the response and any subsequent amendments to the trial site.

Chief Investigators Contact Details:

Name: [name]
Address: The Royal Marsden NHS Foundation Trust
[name]
[name]
Email: [contact]

[name]
Beatson West of Scotland Cancer Centre
[name]
[name]
[contact]

9 DATA ANALYSIS AND STATISTICAL CONSIDERATIONS

9.1 Statistical Analyses

The final analysis will be conducted after one of the following conditions is met.

- The trial is terminated early (for example, due to toxicity).
- All patients have had the opportunity for treatment and have completed their 'off-study' visit.

Once one of the conditions is met, a data cut-off date will be established. All patient visits occurring on or before this date will be analysed and summarised in the final clinical study report. Any data collected after this date will be summarised in a supplemental report.

All data will be analysed using the statistical software STATA version 13. Quantitative data will be presented as number of observations, means, standard deviations, minimum and maximum values if normally distributed or median, interquartile range as appropriate. Categorical data will be presented as frequencies and proportions. When appropriate, data will be presented either with 95% confidence intervals or exact binomial confidence intervals. Baseline characteristics will be summarised for all enrolled patients. Patients who died or withdrew before treatment started or did not complete the required safety observations will be described and evaluated separately. Treatment administration will be described for all cycles. Dose administration, dose modifications or delays and the duration of therapy will be described.

9.1.1 Primary Endpoint

For the primary endpoint of establishing that SBRT 30 Gy in 3# in MPM can be safely combined with pembrolizumab, the toxicity rate will be stated as the proportion of patients who have had a DLT calculated along with an exact binomial confidence interval. All toxicities will be tabulated by type, grade and dose level. This will be assessed for Part A.

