Study Endpoints	
Primary
 
 To confirm that 30 Gy in 3 fractions over 1 week is a safe dose for phase 2 trials (RP2D) of SBRT in MPM combined with pembrolizumab.

	
Secondary
 
 1. To assess the rates of acute toxicity (defined as up to 12 weeks after the last fraction of SBRT) using CTC AE v5.0. 2. To assess the rates of late toxicity (defined as from 12 weeks after last fraction of SBRT in MPM until 28 days after the last dose of pembrolizumab) using CTC AE v5.0. 3. To calculate the ORR and DCR using mRECIST and RESIST 1.1. 4. To calculate the ORR and DCR in epithelioid versus sarcomatoid histological subtype using mRECIST and RESIST 1.1. 5. To assess the frequency of PD-1/PD-L1 expression distribution in responders and non-responders. 6. To measure the PFS and OS at 6 and 12 months. 
Exploratory
 
 1. To characterize tumour infiltrating lymphocytes and tumour antigens in the tumour biopsies. These immunohistochemistry analyses will include, but not necessarily be limited to, the following markers: CD4, CD8, FOXP3, PD-1, PD-L1, and PD-L2. 2. To assess for levels of ctDNA pre- and post- SBRT.

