3.2 Study Endpoints

3.2.1 Primary Endpoint

- To assess the dose limiting toxicity (DLT) of SBRT in MPM at a dose level of 30 Gy given in 3 fractions when combined with pembrolizumab.

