4.2 Treatment Regimen

The study will be conducted in two parts; an initial safety phase (Part A), followed by an expansion cohort (Part B). The initial safety phase (Part A) is based on a 3+3 design such that patients will be treated in a cohort of 3-6 patients. A maximum of 6 patients will be allocated to Part A exploring SBRT 30 Gy in 3 fractions in combination with pembrolizumab. If there is more than one DLT in the first 3 patients or two or more DLTs in the first 6 patients, this treatment combination will be deemed as being unacceptable and it would lead to termination of the study. During the expansion cohort (Part B), 12 patients will have SBRT 30 Gy in 3 fractions with pembrolizumab to obtain additional safety and response data. Maintenance pembrolizumab will continue until disease progression, unacceptable toxicities, the patient withdraws consent to the trial, or the patient has completed 35 cycles of treatment. A maximum of 18 patients will be treated in the study.

All patients will receive pembrolizumab on cycle (C) 1 day (D) 1, in Part A and B of the study. All patients will receive SBRT on C1D15, C1D17 and C1D19, as per SBRT protocol (See Appendix 3). Patients in part A will receive SBRT 30 Gy in 3#. Patients in Part B will receive 30 Gy in 3 fractions if considered safe after part A. All patients in Part A and Part B will receive pembrolizumab dosed at 200 mg every 3 weeks, until disease progression, unacceptable toxicities, the patient withdraws consent from the trial or the patient has completed 35 cycles of treatment.

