5.3 Patient Replacement Strategy

Additional patients may be enrolled in a given cohort to ensure that the required number of evaluable patients in each cohort is achieved. A patient that discontinues the trial for progressive disease within 3 months of the last dose of radiotherapy will not be evaluable for DLTs and therefore will need to be replaced. A patient that discontinues the trial for a drug-related AE will not be replaced and will be counted in the evaluable population of patients for the respective cohort. However, patients found to have active pneumonitis on C1D1 of pembrolizumab or day 1 of radiotherapy will be removed from the trial and can be replaced. Also patients who

do not reach follow-up 3 months post completion of SBRT for MPM for reasons other than progression or toxicity can be replaced by new patients in that cohort to ensure there is a minimum of 3 (or 6 if required) patients in each cohort.

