6 STUDY PLAN AND PROCEDURES

6.1 Study Schedule

From study entry, patients will be assessed every 21 days, prior to the administration of each dose of pembrolizumab. During week 3 of SBRT for MPM, patients will have an additional clinical review. Patients will continue to be assessed and stay on pembrolizumab until they have disease progression, suffer unacceptable toxicities, withdraw, the study ends or have completed 35 cycles of pembrolizumab. Treatment beyond progression or 35 cycles needs to be discussed with the study sponsor and MSD. Patients will be required to attend a safety visit 30 days after their last dose of pembrolizumab.

If the patient has not progressed at the last dose of pembrolizumab they will be reviewed every 9 weeks until the start of new anti-cancer therapy, disease progression, death, withdrawal or end of the study. Patients that have progressed or begin a new anti-cancer treatment will enter into the survival follow up phase and an update will be sought every 12 weeks to assess for disease status until death, withdrawal of consent, or the end of the study, whichever occurs first. Survival follow up can be done over the phone.

The schedule of assessments to be performed at each visit is summarised in Table 3. Individual trial procedures are described in detail below. It may be necessary to perform these procedures at unscheduled time points if deemed clinically necessary by the Investigator. Furthermore, additional evaluations/testing may be clinically indicated for reasons related to patient safety. In some cases, such evaluation/testing may be potentially sensitive in nature (e.g., HIV, Hepatitis B, Hepatitis C, etc.) and will be performed in accordance with local regulations.

Table 3: Study Schedule of Assessments

Trial Phase:	Screening period	Initial phase			Maintenance phase DLT period (Pembrolizumab 200 mg q3wkly)			Maintenance phase ⁽¹⁰⁾ Beyond DLT period (Pembrolizumab 200 mg q3wkly)			End of Treatment (If applicable)	Post-Treatment				
		Radiotherapy phase (30 Gy 3#)			C2, D1	C3, D1	C4, D1	C5, D1	C6, D1	C7, D1	C8, D1	C X ¹⁰ , D1	Discontinuation of Pembrolizumab	Safety Follow- up (SFU)	Follow Up	Survival Follow Up
		C1, D1	C1, D15	C1, D17										30 days after last dose	Every 9 weeks from SFU	Every 12 weeks from SFU
Treatment Cycle/Title:					±3	±3	±3	±3	±3	±3	±3	±3	±3	±7	±7	±7
Scheduling (Day):	-28 to -1															
Informed Consent	X															
Inclusion/Exclusion	X															

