9.1.2 Secondary Endpoints

Acute and late toxicity data will be tabulated by type, grade and dose level with the number, proportions and frequencies of grades 1-4 and grade 3-4 grades reported. The duration of clinical benefit assessed by overall response rate (ORR) defined as complete response (CR) or partial response (PR) and disease control rate (DCR) defined as CR, PR or stable disease (SD) using modified RECIST (Appendix 6) and RECIST 1.1 will be calculated as a proportion of total treated with a 95% confidence interval. Response rates (ORR and DCR), will be calculated as proportions for all patients and in the epithelioid and sarcomatoid histological sub-type giving associated 95% confidence intervals. Any difference in response rates (for ORR and for DCR) between the two sub-types will be compared using a chi squared or Fisher's exact test as appropriate. These will be evaluated for Part A and Part B and for overall. PD-L1 staining is referred to as tumour proportion score, reported as a percentage from 0–100%. It is classed as weakly positive (1 – 49%); strongly positive if >50%; and negative if <1%. The effect of PD-L1 expression on response rates will be measured using the proportion

of patients recorded to be weakly positive, strongly positive or negative and tested using a Chi Squared or Fisher's exact test for proportions on expression level between responders and non-responders. PFS will be measured from the start of radiotherapy until radiological or clinical evidence of progression or death and will be censored at date of last follow-up for surviving patients. OS will be measured from the start of radiotherapy until death and will be censored at date of last follow-up for surviving patients. Duration of response (DOR) will be measured from the date of first response until radiological or clinical evidence of progression or death and will be censored at date of last follow-up for surviving patients. Median PFS, OS and DOR will be calculated using Kaplan-Meier methods giving associated 95% confidence intervals, respectively. PFS, OS and DOR rates at 6 and 12 months will be presented with associated 95% confidence intervals. PFS, OS and DOR will be assessed for overall i.e. Part A and Part B combined. Unless otherwise stated, all secondary endpoints will be analysed for Part A, Part B and overall.

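### The primary DLT rate is estimated from Part A alone (6 patients), although all 18 patients receive the same regimen with the same 12-week DLT window

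*Protocol*

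**What the plan says.** Section 9.1.1 states that "the toxicity rate will be stated as the proportion of patients who have had a DLT calculated along with an exact binomial confidence interval". It closes with the restriction "This will be assessed for Part A".

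The rest of the protocol frames the question more widely:

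- Section 3.2.1 gives the primary endpoint as "To assess the dose limiting toxicity (DLT) of SBRT in MPM at a dose level of 30 Gy given in 3 fractions" combined with pembrolizumab. It names no part of the trial, and neither does the primary objective in 3.1.1.
- The Trial Summary words the primary endpoint as the conclusion to be reached: "To confirm that 30 Gy in 3 fractions over 1 week is a safe dose for phase 2 trials (RP2D").
- Section 4.2 and Tables 1 and 7 give both parts the same SBRT and the same pembrolizumab. Section 4.2 defines the DLT period for the study as 12 weeks from the last SBRT dose. Of Part B it says that "12 patients will have SBRT 30 Gy in 3 fractions with pembrolizumab to obtain additional safety and response data".
- Section 9.1.2 closes with "Unless otherwise stated, all secondary endpoints will be analysed for Part A, Part B and overall". Section 9.1.3 gives the exploratory endpoints the same three-way scope.

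The primary endpoint is thus the only one whose analysis is confined to the first cohort.

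**The concern.** Part A is a 3+3 gate, and reading it out separately is right for the decision to expand. The weakness is that the gate sample is also the only DLT estimate behind the final claim of a safe phase 2 dose.

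This has two consequences. First, precision: up to 12 of 18 identically treated patients contribute nothing to the primary estimate. Second, selection: once Part B has opened, Part A is known to have had at most one DLT, so its proportion is too low on average. The Part B patients are free of that selection.

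The secondary acute-toxicity tables cover Part B over the same 12 weeks, by type and grade. They do not apply the DLT definition of section 4.2.1, for example relatedness to the combination or change in MRC dyspnoea score, so a DLT rate cannot be read from them.

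**Working it through.** **Inputs.** Part A has at most 6 patients and Part B has 12 (sections 4.2 and 9.2). The stated maximum reproduces: 6 + 12 = 18. Part B opens after 0 or 1 DLT in 6 (section 4.2.1). The protocol states no target DLT rate. Section 9.1 attaches no level to exact intervals, so two-sided 95% is assumed here.

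**Step 1: precision.** The Clopper-Pearson limits for x DLTs in n patients are

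- lower = Beta quantile(0.025; x, n − x + 1), or 0 if x = 0
- upper = Beta quantile(0.975; x + 1, n − x)

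| Patients | DLTs/n | Estimate | Exact 95% CI |
|---|---|---|---|
| Part A | 0/6 | 0% | 0 to 45.9% |
| Part A | 1/6 | 16.7% | 0.4 to 64.1% |
| Part B | 0/12 | 0% | 0 to 26.5% |
| Part B | 3/12 | 25.0% | 5.5 to 57.2% |
| Part B | 4/12 | 33.3% | 9.9 to 65.1% |
| A + B | 0/18 | 0% | 0 to 18.5% |
| A + B | 3/18 | 16.7% | 3.6 to 41.4% |
| A + B | 4/18 | 22.2% | 6.4 to 47.6% |

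The two Part A rows are the only primary results possible once Part B has opened. At the same observed rate of 16.7%, the interval narrows from 0.4 to 64.1% (n = 6) to 3.6 to 41.4% (n = 18). At a 90% level the limits are 0 to 39.3% for 0/6, 0.9 to 58.2% for 1/6 and 0 to 15.3% for 0/18, so the picture does not depend on the level.

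**Step 2: selection.** Two or more DLTs in the first 3 imply two or more in 6, so for a true rate p

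- P(Part B opens) = (1 − p)^6 + 6p(1 − p)^5
- E[Part A proportion | opens] = p(1 − p)^5 / P(opens) = p / (1 + 5p)
- E[pooled proportion | opens] = (6 × E[A | opens] + 12p) / 18

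At p = 0.25:

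- P(opens) = 0.178 + 0.356 = 0.534
- E[A | opens] = 0.25 / 2.25 = 0.111
- E[pooled | opens] = (0.667 + 3) / 18 = 0.204

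| Assumed true rate | P(Part B opens) | Mean Part A, given open | Mean A + B, given open | Mean Part A, all outcomes |
|---|---|---|---|---|
| 10% | 88.6% | 6.7% | 8.9% | 10.8% |
| 20% | 65.5% | 10.0% | 16.7% | 22.6% |
| 25% | 53.4% | 11.1% | 20.4% | 28.5% |
| 33.3% | 35.1% | 12.5% | 26.4% | 38.3% |

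The last column counts a stop at 3 patients as x/3. Those means lie above the truth, so the low bias arises only when Part B opens.

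**Step 3: an example.** Suppose there are 0/6 DLTs in Part A and 4/12 in Part B. The planned primary result is 0% (0 to 45.9%). Part B alone gives 33.3% (9.9 to 65.1%), and all 18 give 22.2% (6.4 to 47.6%).

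**The case against.** The restriction can be read as deliberate. The progression rules, the committee reviews after the 3rd and 6th patients, the DLT termination criterion in 4.5.1 and the analysis timing in 9.1.4 all refer to Part A, and confining the formal DLT readout to the 3+3 cohort is conventional. Section 3.2.1 names no population and 9.1.1 supplies one, so the two do not strictly contradict each other. This defends Part A as the gate. It does not justify leaving the later patients out of the only DLT estimate.

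Part B safety is not ignored. Grade 3-4 acute toxicity is reported for Part A, Part B and overall, and most DLTs would appear there. The general safety termination criterion (4.5.1) and Safety Review Committee oversight (11.9) also continue. All of this stands, but none of it yields a DLT proportion. One qualification is fair: 4.2.1 counts related non-haematological toxicity of grade 3 or higher in general before listing items with a 7-day persistence condition, so persistence may separate DLTs from tabulated events less than it first appears.

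Two pieces of textual support are weak, and the point does not rest on them. Section 5.3 speaks of evaluable patients in each cohort but then gives cohort sizes of 3 or 6, which fit Part A. Table 3 has a DLT-period column in one shared schedule, which does not show that DLTs are to be adjudicated in Part B.

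Finally, the conditional bias is a general property of such a gate, the 25% rate is illustrative, pooling leaves some bias, and no stated go/no-go decision would change. Each of these is true. The gain is in the primary safety estimate itself.

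**Conclusion.** The point holds. Section 9.1.1 fixes the population of the primary analysis, so this is a stated choice and not a detail left to a later plan. It sets aside up to 12 of 18 patients treated at the same dose.

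If Part B opens, the primary result can only be 0% or 16.7%, with an upper 95% limit of 45.9% or 64.1%. Using all 18 would bring the upper limit after no DLTs down to 18.5%. At an assumed true rate of 25%, the selected Part A estimate averages 11.1% and the pooled estimate 20.4%.

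These figures assume a 95% level, a common DLT rate in both parts, and 6 and 12 evaluable patients. No hazard to patients is claimed, because the gate and the safety oversight are unaffected. The plan should be amended because its main safety conclusion would otherwise rest on a small and favourably selected sample.

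**What to change.** Leave the Part A rule and its separate readout unchanged. Amend section 9.1.1 to report the DLT proportion with an exact 95% CI, level stated, for:

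- all DLT-evaluable patients at 30 Gy in 3 fractions (Parts A and B, up to 18)
- Part A alone
- Part B alone (12 patients, free of the gate selection)

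State that the DLT criteria of section 4.2.1 are applied to and recorded for Part B patients, and note that the pooled figure is conditional on Part A having passed.

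The cost is low. No patients or visits are added, and AE grading already takes place. The extra work is DLT adjudication for up to 12 patients. A CRF field may be needed, because section 8.2 records causality against the study medication while 4.2.1 requires relatedness to the combination; that mismatch already affects Part A. This should be settled before Part B data are collected, since DLTs may be hard to classify afterwards. The pooled result will come later than the Part A readout and keeps some low bias (20.4% against 25% in the illustration), which the separate Part B row makes visible.
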